5.3 Biopsy Population

The biopsy population will include all randomized subjects who receive at least 1 dose of allocated study drug and have both baseline and end of studies biopsies from at least 8 glomeruli. The biopsy population will be used for all biopsy analyses.

5.4 Pharmacokinetic Population

The pharmacokinetic population will include all randomized subjects who receive at least 1 dose of allocated study drug and have at least one plasma sample tested for R406. The PK population will be used for all PK analyses.

5.5 Treatment Groups for Analysis

For descriptive summaries, the following treatment groups will be used, unless otherwise indicated.

- Placebo (all placebo groups)
- 100 mg bid fostamatinib group
- 150 mg bid fostamatinib group
- Combined fostamatinib group

For comparisons of treatment differences in the analyses of efficacy endpoints, estimates of the following contrasts will be provided, unless otherwise indicated:

- Combined fostamatinib group vs placebo
- 150 mg bid fostamatinib group vs placebo
- 100 mg bid fostamatinib group vs placebo

For all the by-subject listings, the randomized treatment group will be presented.

5.6 Adjustments for Covariates

The randomization stratification factors and the baseline values of the response variables will be included in the statistical analysis model as covariates.

5.7 Multicenter Considerations

Study site will not be included as a factor in the statistical models

5.8 Multiplicity Considerations

No adjustments for multiplicity will be applied

6. Analytic Definitions

Age at Baseline is the last non-missing age collected before the first dose of study treatment.

Body Mass Index is calculated as $(\text{Weight in kg}/(\text{Height in meter})^2)$. The last non-missing weight and height collected before the first dose of study treatment will be used to calculate the baseline BMI.

Baseline Measurements will be the last measurement for the corresponding variable prior to the first randomized dose at Visit 2. For analysis of the primary efficacy endpoint, the main analysis will be performed with baseline defined as the average between Visit 2 and the most recent screening value prior to Visit 2 (a secondary analysis, with the Visit 2 value alone as baseline, will be performed).

Study Day will be the number of days from first dose date of study drug for the assessments prior to the first dose date to assessment date. That is:

$$\text{Study Day of post-dose assessment} = \text{Assessment Date} - \text{First Dose Date} + 1.$$

$$\text{Study Day of pre-dose assessment} = \text{Assessment Date} - \text{First Dose Date}$$

Pre-treatment assessments could be up to 180 days prior to baseline. If there are more than two pre-treatment assessments for a subject, the last assessments will be used for the analyses related to 'pre-treatment'. Post-treatment assessments will be the assessments after the first dose of study drug. If there are more than two post-treatment assessments for a subject within an analysis visit, the last assessment that is closest to the scheduled study day will be used for the analyses related to 'post-treatment'.

Study Drug Exposure is calculated as number of days from first dose day to last. That is:

$$\text{Study Drug Exposure} = \text{Last Study Drug Date} - \text{First Study Drug Date} + 1.$$

Study Drug Compliance (%) for a subject is calculated as: $100 * (\text{total number of tablets dispensed during the double-blind treatment period} - \text{total number of tablets returned during the double-blind treatment period}) / \text{total number of tablets the subject was supposed to taken during the double-blind treatment period per protocol}$:

$$\text{Compliance (\%)} = 100 \times (\sum_{i=1}^6 D_i - \sum_{i=1}^6 R_i) / \sum_{i=1}^6 T_i * P_i$$

where:

i = study drug dispensation/return visit interval, $i = 1$ to 6

D_i = total number of tablets dispensed for visit interval i

R_i = total number of tablets returned for visit interval i

$T_i = 2$ for bid dosing and $=1$ for qd dosing, for visit interval i

P_i = total number of days in visit interval i .

The total number of tablets that were supposed to be taken during the double-blind treatment period excludes the number of tablets not taken due to a dose interruption. If a patient fails to return a study drug kit dispensed during the double-blind treatment period, then study drug compliance is considered to be missing.

Baseline sPCR: Two baseline sPCR value will be used in the analysis. In primary efficacy analysis, the baseline sPCR is defined as the average of non-missing value between Visit 2 and the most recent screening value prior to Visit 2. If only one non-missing sPCR is available, this value will be used as baseline.

A **Treatment-Emergent Adverse Event (TEAE)** is any adverse event that emerges on or after first dosing and prior to the end of follow-up (having been absent prior to treatment) or worsens relative to the pre-treatment state.

Hy's Law criteria are: concurrent aspartate aminotransferase (AST) or alanine aminotransferase (ALT) $\geq 3x$ upper limit of normal (ULN) with total (and/or direct/conjugated) bilirubin (TBL) $> 2x$ ULN and alkaline phosphatase (ALP) $< 2x$ ULN, and no other reason can be found to explain the combination of increased aminotransferase and serum total bilirubin, such as viral hepatitis, alcohol abuse, ischemia, preexisting liver disease, or another drug capable of causing the observed injury.

Prior Medications will be defined as the medications used prior to the first dose of study drug. If the medication is used both prior to and on/after the first dose of study drug, the medication is both prior medication and concomitant medication.

Concomitant Medication will be defined as the medications used on/after the first dose of study drug.

7. Statistical Methods

The statistical analysis of the data obtained from this study will be performed using SAS® version 9.4 or higher. All inferential tests will be 2-sided and will be performed using a type I error rate of 5%, unless otherwise indicated.

Descriptive statistics for continuous variables will be presented with the, number of non-missing observations, mean, standard deviation, 25th percentile, median, 75th percentile, minimum and maximum, unless otherwise specified. In general, the same number of decimal places as in the raw data will be presented when reporting minimum and maximum, 1 more decimal place than in the raw data will be presented when reporting mean and median, and 2 more decimal places than in the raw data will be presented when reporting SD. If the raw data have 3 decimals or more, 3 decimals will be presented for mean, median, minimum and maximum, and SD.

For categorical data, descriptive statistics will be presented with the number and percentage of subjects in the various categories of the endpoint. One decimal will be presented for percentages. Percentages equal to 100 will be presented as 100%.

All data collected in clinical database will be listed in by-subject listings for subjects in the ITT population (i.e. the randomized subjects), unless otherwise indicated.

7.1 Subject Disposition and Protocol Deviations

Subject disposition will be summarized by treatment as number of screened subjects, randomized subjects, the number and percentage of subjects in each analysis population, and the number and percentage of subjects who complete the study or withdraw (the latter summarized by reason for withdrawal).

Subject disposition will also be summarized by Site ID. This summary will include the number of subjects treated, completed and discontinued early by each part of the study.

Major protocol deviations collected on case report forms will be tabulated by treatment and the deviation category (Enrollment Criteria, Non-Compliance, Laboratory, Dosing, Visit Schedule, Visit/Procedure Requirement, Concomitant Medication, Regulatory, and Other) in the ITT population. The final protocol deviation (i.e., unplanned deviation) and protocol exemption (i.e., planned deviation) data will be reported in the Listing outputs.

7.2 Demographics and Baseline Characteristics

Demographics and baseline characteristics will be summarized by treatment in the ITT population.

Medical history will be coded using the Medical Dictionary for Regulatory Affairs (MedDRA), using the latest version available at the time of the interim analysis, as specified in the Data Management Plan (DMP). The medical history conditions will be summarized by treatment, system organ class and preferred term in the ITT population.

Prior IgA Nephropathy and Concomitant medications will be coded using the latest version of the World Health Organization Drug Dictionary (WHO-DDE) available at the time of the IA, as specified in the DMP. Prior and concomitant medications will be summarized by treatment,

anatomical therapeutic chemical classification (ATC) level 2 term and preferred term in the ITT population. Additionally, the number and percentage of Subjects who changed anti-hypertensive regimen during the treatment period, either in medication or dose of medication, will be summarized by study stage and listed. Anti-hypertensive medications are medications with the following ATC codes:

- CO2: Anti-hypertensives
- CO3: Diuretics
- CO4 Peripheral Vasodilators
- CO7: Beta blocking agents
- CO9: Agents acting on the renin-angiotensin system.

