3.5.1 Blood Pressure Elevation

Blood pressure elevation, a well described adverse effect of treatment with fostamatinib, may reflect off-target inhibition of vascular endothelial growth factor receptor-2 (VEGFR-2).

In RA clinical trials, increases in blood pressure (mean ~2-4 mmHg) generally occurred early and were responsive to anti-hypertensive treatment. Patients with a history of hypertension

appeared to be at greater risk of developing an increase in blood pressure and experienced higher mean increases (~5-9 mmHg). A few patients have experienced severe elevated blood pressure (≥ 180 systolic and ≥ 110 diastolic). In these studies the blood pressure effect has been reduced or eliminated over time by timely and effective anti-hypertensive treatment.

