10.3.2 Secondary Efficacy Endpoints

The safety population will include all randomised subjects who received at least 1 dose of the allocated study drug. The safety population will be analyzed for all safety assessments. The subjects will be analyzed as treated.

Secondary efficacy endpoints related to proteinuria will be measured by sPCR (as is the case for the primary efficacy endpoint).

All secondary efficacy endpoints will be analyzed using both the ITT and PP populations. Additionally, the primary efficacy endpoint will be analyzed using the PP population as a sensitivity analysis. No adjustments will be made for multiplicity.

The following secondary endpoints will be analyzed using an ANCOVA model which includes the treatment group and presence/absence of endothelial hypercellularity at baseline as factors, with mean estimates of the variable adjusted for the baseline value:

- Mean change from pre-treatment to post-treatment in mesangial hypercellularity on renal biopsies.
- Mean change from pre-treatment to post-treatment in endocapillary hypercellularity on renal biopsies.
- Mean change from pre-treatment to post-treatment in segmental sclerosis/adhesion on renal biopsies.
- Mean change from pre-treatment to post-treatment in global glomerulosclerosis score on renal biopsies
- Mean change from pre-treatment to post-treatment in tubulointerstitial scarring on renal biopsies.
- Mean change from Baseline (Visit 2) of eGFR at 12 weeks (Visit 7).
- Mean change from Baseline (Visit 2) of eGFR at 24 weeks (Visit 9).
- Mean change from Baseline (Visit 2) of proteinuria at 12 weeks (Visit 7).
- Shift in haematuria (dipstick test) from Baseline (Visit 2) at 12 weeks (Visit 7).

- Shift in haematuria (dipstick test) from Baseline (Visit 2) at 24 weeks (Visit 9).

Estimates will be provided for the following contrasts: 1) combined fostamatinib group vs. placebo; 2); 150 mg fostamatinib group vs. placebo; and 3) 100 mg fostamatinib group vs. placebo.

Fisher's exact test will be used to assess whether the percentage of subjects who meet the following criteria differ between the pooled fostamatinib and placebo groups:

- Have a $\geq 30\%$ reduction in sPCR from Baseline (Visit 2) to Week 24 (Visit 9)
- Have sPCR $< 50\text{mg}/\text{mmoL}$ at Week 12

The 95% CIs for the percentages will also be provided.

Shift tables will display the change in category from Baseline (Visit 2) to Week 24 (Visit 9) for the following categorical parameters:

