If the BP is found to be 160-179 systolic or 100-109 diastolic at any visit after randomisation:

- Continue study drug at assigned dose level.
- Adjust anti-hypertensive therapy.
- Reassess BP twice weekly.
- If, after 1 week, the BP remains \geq 160-179 systolic or \geq 100-109 diastolic despite aggressive antihypertensive therapy, interrupt study drug administration.
- Increase anti-hypertensive medications until control is established.
- Restart study drug (at a reduced dose, see Table 1) when blood pressure $<$ 140/90 mm Hg.

If BP is \geq 140 mmHg systolic and/or \geq 90 mmHg diastolic but below 160 systolic or 100 diastolic at any visit after randomisation:

- Continue study drug at assigned dose level.
- Repeat blood pressure assessment within 1 week.
- If blood pressure remains above \geq 140 mmHg systolic and/or \geq 90 mmHg diastolic after 1 week adjust antihypertensive therapy.
- Continue to monitor BP weekly until control is established.
- If BP remains \geq 140 mmHg systolic and/or \geq 90 mmHg diastolic for more than 8 weeks, despite aggressive antihypertensive therapy, reduce dose of study drug (see Table 1).

REFERENCES

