3.2 Determination of Sample Size

A sample size of 25 evaluable subjects in each of the 3 treatment groups will have an 80% power to detect a 43% reduction in sPCR from Baseline to Week 24 between the pooled fostamatinib and placebo groups, using a 2-sided t-test with $\alpha = 0.05$ and log-transformed data. This calculation assumes that the 3 treatment groups have the same mean and standard deviations of urinary protein/creatinine ratio and coefficient of variation of 0.923 at Baseline and that the values for the placebo group remain constant over 24 weeks. Treatment allocation ratio will be 1:2 for the placebo: combined fostamatinib groups

Table 1 Study Treatment

Treatment Group	Number of Subjects	Dose
C	25	Placebo bid
A	25	Fostamatinib 100 mg bid
B	25	Fostamatinib 150 mg bid

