7.4.2 Sensitivity Analyses

While the inferential analysis methodology will remain unchanged for sensitivity analyses of the primary endpoint, one method of imputing missing data will be performed before inferential analysis:

The LOCF procedure in the ITT population – This analysis will use an ANCOVA model. The ANCOVA model will include both the treatment group and the presence/absence of endothelial hypercellularity at baseline as factors and adjust for the sPCR at baseline (as a covariate). Dependent variable is change from baseline to Week 24 in sPCR. Missing Week 24 data will be imputed using the LOCF procedure. Pre-treatment values will not be carried forward.

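### Antihypertensive changes, which may be more frequent on fostamatinib, are tabulated by an undefined study stage without calcium channel blockers, and no primary-endpoint analysis addresses them

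*SAP*

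**What the plan says.** **Blood pressure.** Protocol 3.5 describes a dose-dependent effect of fostamatinib on blood pressure. Section 3.5.1 puts the mean rise in the rheumatoid arthritis trials at about 2-4 mmHg, and at about 5-9 mmHg in patients with a history of hypertension. Appendix 4 calls for prompt treatment. Section 7.6.1 and Appendix 4 hold the ACEi/ARB dose fixed from Visit 2 to Visit 9 and name diuretics, calcium channel blockers and beta-blockers as the agents to add.

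**Reporting of changes.** SAP 7.2 reports a count and percentage for those "who changed anti-hypertensive regimen during the treatment period, either in medication or dose of medication, will be summarized by study stage and listed". The sentence before it summarises prior and concomitant medications by treatment. The antihypertensive class list has five entries: C02 antihypertensives, C03 diuretics, C04 peripheral vasodilators, C07 beta-blockers and C09 renin-angiotensin agents. Study stage is used again in SAP 7.6.2 and is defined in neither place.

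**Primary endpoint.** In SAP 7.4.2 the inferential method is unchanged and "one method of imputing missing data will be performed before inferential analysis": LOCF in the ITT population. The other variants are the Visit 2 baseline (SAP section 6) and subgroups set by RAS-blockade duration and baseline sPCR (SAP 7.4.3). Protocol 10.3.2 also states that "the primary efficacy endpoint will be analyzed using the PP population as a sensitivity analysis". The SAP defines no per-protocol population and does not mention that analysis.

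**The concern.** The drug has a known pressor effect, the protocol prescribes a response to it, and the primary endpoint is proteinuria. If added agents lower sPCR and are used more on fostamatinib, part of any difference from placebo could come from the added treatment. A reader of a positive proof-of-concept result would ask two questions: did add-on use differ between arms, and does the effect hold without values measured after a change? The plan has one summary of regimen change. It may not compare arms, and it leaves out a class that the protocol tells sites to use. For the second question the plan has no analysis.

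**Working it through.** **1. The plan's own figure.** SAP 3.2 has "A sample size of 25 evaluable subjects in each of the 3 treatment groups" giving "80% power to detect a 43% reduction in sPCR from Baseline to Week 24 between the pooled fostamatinib and placebo groups", with a coefficient of variation of 0.923, a two-sided t-test at 0.05 and 1:2 allocation.

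- Log-scale SD = sqrt(ln(1 + 0.923²)) = 0.785.
- Design effect = -ln(1 - 0.43) = 0.562.
- Placebo subjects needed for 80% power: 23 (normal approximation) or 24 (noncentral t, power 80.6%).
- Power at 25 versus 50: 83.2% (normal) or 82.2% (noncentral t).

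The stated sample size is reproduced and is not in dispute.

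**2. What the documents give on add-on use.** They give no rate by arm. Protocol 3.1 links only renin-angiotensin blockers to lower proteinuria, and gives no effect size for the add-on classes. Any size must therefore be assumed.

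**3. Illustration.** Let *d* be the excess proportion of add-on users on fostamatinib and *r* the proportional sPCR reduction per user, equal in all arms, with no true drug effect. The log-scale shift is -d × ln(1 - r), and the apparent pooled reduction is 1 - (1 - r)^d. For d = 0.25 and r = 0.20, the shift is 0.25 × 0.223 = 0.056, an apparent reduction of 5.4%. Over a wider range:

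| Assumed excess *d* | Assumed *r* | Apparent reduction | Share of design effect (log scale) | Chance of p < 0.05 with no drug effect |
|---|---|---|---|---|
| 10% | 10% | 1.0% | 2% | 5.0% |
| 20% | 20% | 4.4% | 8% | 5.6% |
| 30% | 30% | 10.1% | 19% | 8.5% |
| 40% | 30% | 13.3% | 25% | 11.3% |
| 40% | 40% | 18.5% | 36% | 18.2% |

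The last column uses the plan's t-test with 25 versus 50 subjects and SD 0.785. If baseline adjustment gives a smaller residual SD, the same shift would produce a higher rejection rate.

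**4. Direction.** The table takes one sign only. Blood pressure rises left untreated could raise sPCR in the active arms, and add-on therapy may do no more than offset a drug-induced rise. The net sign cannot be derived from the documents.

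**5. Can another planned output show new or increased agents by arm?**

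- The concomitant medication table is by treatment. However, SAP section 6 counts any drug used on or after the first dose, including drugs started earlier. The table mixes stable background therapy with new agents and shows no dose increases.
- SAP 5.5 makes treatment groups the default for descriptive summaries unless otherwise indicated. SAP 7.2 names a different grouping for this table, so it is unclear whether the default applies.
- By-subject listings carry the randomised arm. A listing is not a summary by arm.
- Calcium channel blockers will appear in the concomitant medication table, but under the class list they do not count as an antihypertensive change.

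**6. Can a planned primary-endpoint analysis set these changes aside?** LOCF concerns missing values. The Visit 2 baseline analysis and the subgroups do not involve treatment changed after baseline. None of them does so.

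**The case against.** **Size.** Entry requires blood pressure controlled to 130/80 or below. Even a 9 mmHg mean rise from that limit reaches only 139/89, below the 140/90 level in Appendix 4. At 140-159/90-99, Appendix 4 has the reading repeated within a week and therapy adjusted only if the rise persists. The illustration is thus a guess, and its 20%/20% case moves the false-positive rate only from 5.0% to 5.6%. This largely stands. Individual subjects will exceed the mean, though, and Appendix 4 asks sites to consider keeping blood pressure below 130/80 in renal insufficiency.

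**Arm information.** A reader might infer that the trial could not show at all whether add-on use differed between arms. The documents do not support that: concomitant medications are tabulated by treatment and listings show the arm. What is missing is a clear summary by arm of new or increased agents.

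**Per-protocol analysis.** A reader might also infer that the SAP, by dropping this analysis, removed the one that would strip out add-on effects. It would not have done so. Protocol 10.2 excludes major violations, and adding an agent as directed is not one, so those subjects would stay in. At most, ACEi/ARB or steroid changes would be excluded, if blinded review classed them as major.

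**Supportive analysis.** It targets a hypothetical effect, and ITT including protocol-directed care is a legitimate primary analysis. Both points are fair, and ITT should stay primary. It could also be said that the planned imputation has no category for subjects who stay on study after an add-on. That does not hold: SAP 7.4.1 already treats completers with missing visit data as missing at random.

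**Conclusion.** The concern holds as a gap in reporting and in supportive analysis. The only planned summary of antihypertensive change uses an undefined grouping and omits a class the protocol names, and no primary-endpoint analysis addresses such changes. Higher add-on use in the active arms is a plausible inference from the pressor effect and the protocol's instructions, but it is not documented.

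The size is conditional. The apparent reduction is 1% to 18.5% over the assumed range, and 5.4% at 25 points of excess use with a 20% effect per user. These figures assume no true drug effect and no opposing influence on sPCR. They do not show that a fall in sPCR on fostamatinib would be spurious.

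The missing per-protocol analysis is a separate, unexplained difference between protocol and SAP.

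**What to change.** 1. **SAP 7.2.** Summarise antihypertensive regimen changes by randomised treatment group. Split by study stage only if the term is defined. Add the calcium channel blocker class to the list.
2. **SAP 7.4.2.** Add one supportive analysis. In every arm, set sPCR to missing from the first new or increased antihypertensive, ACEi/ARB change, steroid change or prohibited immunosuppressant. Impute with the planned multiple-imputation model, treating subjects who remain on study as missing at random within their arm group, as SAP 7.4.1 does for completers with missing data. Keep the ITT analysis as primary.
3. **Separately,** restore the per-protocol sensitivity analysis from protocol 10.3.2 or state why it was dropped. This does not replace item 2.

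**Cost.** SAP wording, one table and one supportive run, plus the per-protocol run if restored. All use data already collected, and trial conduct does not change. The supportive analysis has fewer observed Week 24 values and wider intervals, and it conditions on events after randomisation, so it is supportive only. As a rough guide, if add-on users were simply excluded (assumed 20-40% of active and 10% of placebo subjects), 22.5 placebo versus 40 to 30 active subjects would remain, and t-test power for a 43% reduction would fall from 82% to about 76-71%.

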7.6.1 Required Medications: Angiotensin Blockade

Subjects should be taking a maximum tolerated approved dose of an ACEi or ARB before an additional anti-hypertensive agent is added. Subjects should remain on the same dose of ACEi or ARB during the dosing period (Visits 2-9). If additional anti-hypertensive therapy is required, other agents (beta-blockers, calcium channel blockers, or diuretics) should be added.

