Appendix 4: Guideline for Management of Hypertension

Treatment with fostamatinib may cause blood pressure elevation in certain subjects. It is believed that this effect is a result of off-target activity against the VEGFR2 receptor. Increases in BP have proven to be amenable to treatment, generally without a requirement for study drug interruption. **Subjects with elevated blood pressure should receive prompt treatment.**

Blood pressure for all subjects should be kept below 140/90 mmHg; for subjects with increased cardiovascular risk or renal insufficiency, consideration should be given to maintaining the blood pressure below 130/80 mmHg. Subjects should remain on the same dose of ACEi or ARB during the dosing period (Visits 2-9). If additional anti-hypertensive therapy is required, other agents (beta-blockers, calcium channel blockers, or diuretics) should be added. In previous clinical studies evaluating fostamatinib, the following anti-hypertensive agents (alone or in combination) have proven effective in managing BP:

- Angiotensin converting enzyme inhibitors
- Angiotensin receptor blockers
- Calcium channel blockers
- Beta-blockers
- Diuretics

If aggressive and appropriate anti-hypertensive therapy does not control BP (< 140/90), it may be necessary to reduce the dose of study medication.

Management Algorithm for Elevated Blood Pressure

Follow the dose adjustment guidelines in Table 1 when adjusting the dose of study medication.

Table 1: Dose Adjustment

Starting Dose	Dose Level -1	Dose Level -2	Dose Level -3 ^a	Dose Level -4 ^a
100 mg PO bid	150 mg PO qd	100 mg PO qd	Discontinue	-----
150 mg PO bid	100 mg PO bid	150 mg PO qd	100 mg PO qd	Discontinue

^a The Sponsor's Medical Monitor should be consulted prior to consideration of dose modification to levels -3 or -4.

The following should result in prompt discontinuation of study medication:

- The blood pressure cannot be brought under control despite best efforts at blood pressure management.

If BP \geq 180/110 mmHg at any time after randomisation:

- Temporarily withhold dosing with study drug.
- Adjust anti-hypertensive medications.
- Reassess BP twice weekly.
- If a repeat BP \geq 180/110 mmHg despite adjusted anti-hypertensive treatment, permanently discontinue study drug.
- Increase anti-hypertensive medications until control is established.
- Restart study drug (at a reduced dose, see Table 1) when blood pressure $<$ 140/90 mm Hg.

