7.4.3 Subgroup Analysis

Sample size permitting, the primary efficacy analysis will also be conducted for the following subgroups:

1. Time since initial exposure to RAS blockade (< 6 months vs ≥ 6 months from baseline). The initial exposure to RAS blockade (angiotensin II receptor blocker (ARB) or angiotensin converting enzyme inhibitor (ACEI)) will be derived from prior/concomitant medication collected on CRF. The imputed medication start date will be used to calculate the duration of the exposure from baseline.
2. Baseline sPCR: sPCR > 2000 mg/g and sPCR > 3500 mg/g.

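### The SAP's list of anti-hypertensive classes leaves out calcium channel blockers, so the regimen-change count misses subjects whose only change is in that class

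*SAP*

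**What the plan says.** SAP Section 7.2 commits to a number and percentage of subjects whose anti-hypertensive regimen changed during the treatment period, "either in medication or dose of medication", with a matching listing. It then defines the term: "Anti-hypertensive medications are medications with the following ATC codes". Five entries follow: CO2 (anti-hypertensives), CO3 (diuretics), CO4 (peripheral vasodilators), CO7 (beta blocking agents) and CO9 (renin-angiotensin agents). Nothing in the wording marks the list as illustrative, and no other part of the SAP extends it.

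Protocol Section 7.6.1 sets out how background therapy should move during the trial. For the renin-angiotensin class: "Subjects should remain on the same dose of ACEi or ARB during the dosing period (Visits 2-9". For anything further: "other agents (beta-blockers, calcium channel blockers, or diuretics) should be added". Appendix 4 repeats both statements. It also gives a list introduced by the statement that in earlier fostamatinib studies "the following anti-hypertensive agents (alone or in combination) have proven effective in managing BP". Its five items are ACE inhibitors, ARBs, calcium channel blockers, beta-blockers and diuretics. Inclusion criterion 8 names the same three add-on classes.

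**The concern.** The protocol holds one class constant and names three in which additions may be made. The SAP list includes the class meant to stay constant but drops one of the three that may change. Following SAP 7.2 as written, a programmer would classify a subject who was started on a calcium channel blocker in Week 4, and had no other change, as having no regimen change.

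This matters because increased blood pressure is a safety parameter of interest in both documents (Section 4.4 of each), and Appendix 4 of the protocol calls for raised pressure to be treated promptly. Measured pressure can then look controlled because background therapy was intensified. The regimen-change count is the one SAP summary dedicated to showing how many subjects had that therapy altered.

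**Working it through.** The plan states no figure for this count, so there is none to reproduce. The check compares the two texts and then works out the weight of one subject.

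**Add-on classes in protocol Section 7.6.1 and Appendix 4 against the SAP 7.2 list**

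| Protocol add-on class | Entry in SAP 7.2 |
|---|---|
| Beta-blockers | CO7, covered |
| Diuretics | CO3, covered |
| Calcium channel blockers | none |

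Coverage: 2 of 3.

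**Appendix 4 list of agents effective in earlier studies against the SAP 7.2 list**

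| Appendix 4 agent class | Entry in SAP 7.2 |
|---|---|
| ACE inhibitors | CO9, covered |
| ARBs | CO9, covered |
| Beta-blockers | CO7, covered |
| Diuretics | CO3, covered |
| Calcium channel blockers | none |

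Coverage: 4 of 5. Placing ACE inhibitors and ARBs under CO9 follows the SAP's own usage in Section 7.4.3, which groups the two: "The initial exposure to RAS blockade (angiotensin II receptor blocker (ARB) or angiotensin converting enzyme inhibitor (ACEI)) will be derived".

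**Could CO2 act as a catch-all?** Its label is the general word for these drugs. If it covered every drug given for blood pressure, the separate entries for diuretics, beta blocking agents and renin-angiotensin agents would be redundant. The list works class by class, so the label does not bring in "calcium channel blockers".

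**Who is missed.** Only a subject whose sole change is in a drug coded solely as a calcium channel blocker. A subject who also changes a drug in a listed class is still counted. Each error of this kind turns a true change into no change, so the omission biases the count downward.

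**Weight of one missed subject at the planned size** (25 per group, SAP Section 3.2), using 100 × 1/n:

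- one treatment group: 100 × 1/25 = 4.0 percentage points
- combined fostamatinib group: 100 × 1/50 = 2.0 points
- all subjects: 100 × 1/75 = 1.3 points

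The documents give neither a rate of regimen change nor the share confined to calcium channel blockers, so the number of missed subjects cannot be estimated.

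**The case against.** The strongest objection is that very little is lost. The count is descriptive and sits under demographics and baseline characteristics, not under safety. Calcium channel blocker use still appears by treatment in the prior and concomitant medication tables. By-subject listings carry the underlying records with the randomised group (SAP Sections 5.5 and 7). Blood pressure itself is summarised by visit and in shift tables of the highest value (SAP Section 7.6.3). All of this stands and is why the point is minor. It does not fully replace the count. Under SAP Section 6, when a drug is used both before and after first dose, "the medication is both prior medication and concomitant medication". Comparing the two tables therefore shows net new use by arm, but not stops or dose changes during treatment, which the count is defined to capture.

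A second objection concerns the denominator. SAP 7.2 says this count is summarised by study stage, while its neighbours in the same section are summarised by treatment, so 4 points per subject might not be the relevant figure. SAP Section 5.5 makes treatment groups the default for descriptive summaries, and Section 7.6.2 uses the same study-stage phrase for the Hy's law count, so a display by arm is the more natural reading. If the table is not split by arm, 1.3 points applies.

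A third is that class membership depends on a coding dictionary that the documents do not reproduce. That is fair. The omission from the list is certain. Its effect on the count is inferred from class labels, and the conclusion is limited to drugs coded only as calcium channel blockers for that reason.

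**Conclusion.** The concern holds, as a minor one. The definition in SAP 7.2 is wrong as written for what it sets out to count: it omits one of the three add-on classes that the protocol names. The direction of this error is downward; nothing is claimed about the net effect of other features of the definition. Its size is unknown. Each missed subject is worth 4.0 points in a group of 25, falling to 1.3 points if the display pools all 75. These percentages assume the planned group sizes. The consequence is confined to this count and its listing. No endpoint, model or adverse event table changes.

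**What to change.** Add the calcium channel blocker class, with its ATC code from the dictionary version specified in the Data Management Plan, to the list in SAP Section 7.2. The count and its listing will then cover all three add-on classes in protocol Section 7.6.1 and Appendix 4. The cost is one extra line in the definition and one extra code in the program. The medications are already collected, coded and listed, so no new data or change to subject procedures is needed.
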